**Figure 1. Study Schematic**

PBO = placebo; RZB = risankizumab; W = week

### 2.3 Treatment Assignment and Blinding

Each subject will be assigned a unique identification number by the IRT at the screening visit. Subjects who rescreen will use the same unique identification number from the initial screening visit. In addition, the IRT will assign a unique randomization number that will encode each subject's treatment group assignment according to the randomization schedule generated by the statistics department at AbbVie.

At the Baseline visit, subjects meeting eligibility criteria will be randomized in a 2:2:1 ratio to risankizumab 150 mg, risankizumab 300 mg, or matching placebo.

Randomization at Baseline will be stratified by baseline disease severity (moderate [vIGA-AD 3] vs. severe [vIGA-AD 4]) and geographic region (Japan vs. Rest of the World [RoW]).

At the Week 16 visit, subjects receiving placebo in Period A will be re-randomized in a 1:1 Ratio to receive either risankizumab 150 mg or risankizumab 300 mg through Week 52. Subjects originally randomized to risankizumab 150 mg or 300 mg in Period A will stay on their previously assigned treatment through Week 52. There is no stratification at the re-randomization at Week 16.

To maintain the blind, all risankizumab and placebo kits provided for the study will be identical in appearance. AbbVie personnel will remain blinded until the primary analysis at Week 16 is available. The study sites and subjects will remain blinded to treatment assignments for the entire duration of the study.

## **2.4 Sample Size Determination**

Approximately 155 subjects will be randomized to risankizumab 150 mg, risankizumab 300 mg, or placebo in a ratio of 2:2:1 (62 subjects each for the risankizumab 150 mg and 300 mg groups and 31 subjects for the placebo group). Assuming an EASI 75 response rate of at most 15% in the placebo group, this sample size will provide more than 90% power to detect the treatment difference of at least 36% between each risankizumab group and placebo group using a two-sided test at a 0.025 significance level.

## **3.0 Endpoints**

### **3.1 Primary Endpoint(s)**

The primary endpoint is the proportion of subjects achieving at least a 75% reduction from Baseline in Eczema Area and Severity Index (EASI 75) at Week 16.

### **3.2 Secondary Endpoint(s)**

The key secondary endpoints for this study are:

1. The proportion of subjects achieving validated Investigator Global Assessment Scale for Atopic Dermatitis (vIGA-AD) of "0" or "1" (on a 5-point scale) with a reduction from Baseline of  $\geq 2$  points at Week 16.
2. The proportion of subjects achieving a reduction of  $\geq 4$  points in worst pruritus numerical rating scale (NRS) from Baseline to Week 16.

Other secondary endpoints that are not included in the multiplicity testing procedure (see Section 12.0) are listed below and will be evaluated for each of the specified time points:

- Percent change in EASI from Baseline to Week 16, Week 28, and Week 52.
- Proportion of subjects achieving EASI 75 at Week 28 and Week 52.
- Proportion of subjects achieving EASI 50 at Week 16, Week 28, and Week 52.
- Proportion of subjects achieving EASI 90 at Week 16, Week 28, and Week 52.
- Proportion of subjects achieving vIGA-AD of "0" or "1" with a reduction from Baseline of  $\geq 2$  points at Week 28 and Week 52.
- Change in body surface area (BSA) from Baseline to Week 16, Week 28, and Week 52.
- Proportion of subjects achieving 50% improvement in SCORing Atopic Dermatitis (SCORAD 50) at Week 16, Week 28, and Week 52.
- Proportion of subjects achieving SCORAD 75 at Week 16, Week 28, and Week 52.
- Proportion of subjects achieving SCORAD 90 at Week 16, Week 28, and Week 52.
- Proportion of subjects achieving Dermatology Life Quality index (DLQI) of "0" or "1" at Week 16, Week 28, and Week 52.
- Proportion of subjects achieving Children's Dermatology Life Quality index (CDLQI) of "0" or "1" at Week 16, Week 28, and Week 52.
- Proportion of subjects achieving a DLQI improvement of  $\geq 4$  points at Week 16, Week 28, and Week 52 among subjects with a DLQI  $\geq 4$  at Baseline.
- Change in DLQI from Baseline to Week 16, Week 28, and Week 52.
- Change in CDLQI from Baseline to Week 16, Week 28, and Week 52.

- Change in worst pruritus NRS from Baseline to Week 16, Week 28, and Week 52.
- Proportion of subjects achieving a reduction of  $\geq 4$  points in worst pruritus NRS from Baseline to Week 28 and Week 52.

### 3.3 Other Efficacy Endpoint(s)

All variables listed as primary or secondary efficacy endpoints will be analyzed at all visits in addition to those specified above. In addition, the following additional endpoints will be evaluated at all applicable visits:

- Proportion of subjects achieving EASI 100.
- Proportion of subjects achieving vIGA-AD of "0" with a reduction from Baseline of  $\geq 2$  points
- Percent change in SCORAD from baseline.
- Change from Baseline in Patient Oriented Eczema Measure (POEM).
- Proportion of subjects achieving an improvement (reduction) in POEM of  $\geq 4$  from Baseline among subjects with a POEM  $\geq 4$  at Baseline.
- Change from Baseline in Patient Global Impression of Severity (PGIS).
- Proportion of subjects who report symptoms to be "Minimal" or "Absent" for PGIS.
- Proportion of subjects who have "Very much improved" or "Much improved" for Patient Global Impression of Change (PGIC).
- Change from Baseline in Atopic Dermatitis Symptom Scale (ADerm-SS) 7-item total symptom score (TSS-7) and 11-item total symptom score (TSS-11).
- Change from Baseline in ADerm-SS skin pain score.
- Change from Baseline in Atopic Dermatitis Impact Scale (ADerm-IS) domain scores (sleep, emotional state, daily activities).
- Proportion of subjects achieving an improvement (reduction) in ADerm-SS TSS-7  $\geq$  minimal clinically important difference (MCID) from Baseline for subjects with ADerm-SS TSS-7  $\geq$  MCID at Baseline.

- Proportion of subjects achieving an improvement (reduction) in ADerm-SS TSS-11  $\geq$  MCID from Baseline for subjects with ADerm-SS TSS-11  $\geq$  MCID at Baseline.
- Proportion of subjects achieving an improvement (reduction) in ADerm-SS skin pain score  $\geq$  MCID from Baseline for subjects with ADerm-SS skin pain score  $\geq$  MCID at Baseline.
- Proportion of subjects achieving an improvement (reduction) in ADerm-IS sleep domain score  $\geq$  MCID from Baseline for subjects with ADerm-IS sleep domain score  $\geq$  MCID at Baseline.
- Proportion of subjects achieving an improvement (reduction) in ADerm-IS emotional state domain score  $\geq$  MCID from Baseline for subjects with ADerm-IS emotional state domain score  $\geq$  MCID at Baseline.
- Proportion of subjects achieving an improvement (reduction) in ADerm-IS daily activities domain score  $\geq$  MCID from Baseline for subjects with ADerm-IS daily activities domain score  $\geq$  MCID at Baseline.
- Change from Baseline in EuroQoL-5D-5L (EQ-5D-5L).

Of note, MCIDs are planned to be established prior to the primary analysis database lock.

### **3.4 Safety Endpoint(s)**

The following endpoints will be included in the safety analyses:

- Treatment emergent adverse events (TEAEs)
- Serious adverse events (SAEs)
- Areas of safety interest (ASIs)
- Adverse events (AEs) leading to study drug discontinuation
- Vital signs, laboratory tests and electrocardiogram (ECG) parameters.

### **3.5 Additional Endpoint(s)**

The pharmacokinetic endpoints will be analyzed separately and not be covered in this SAP.

## 4.0 Analysis Populations

The following population sets will be used for the analyses.

The intent-to-treat (ITT) population, which includes all randomized subjects, will be used for all efficacy analyses. Subjects will be included in the analysis according to the treatment groups that they are randomized to. Subjects who are randomized to placebo in Treatment Period A and do not continue into Treatment Period B will be excluded from the analysis in Treatment Period B.

The following populations will be used for safety analyses:

- The safety population in Period A is defined as all subjects who are randomized at Baseline and received at least one dose of study drug in Treatment Period A. Subjects are assigned to a treatment group based on the treatment actually received.
- The safety population in Period B is defined as all subjects who received at least one dose of study drug in Treatment Period B. Subjects are assigned to a treatment group based on the treatment actually received.
- An All Risankizumab Treated Population (ALL\_RZB) will consist of all subjects who received at least one dose of risankizumab in the study. This population will be used to provide a comprehensive summary of safety.

For the safety populations, subjects are assigned to a treatment group based on the "as treated" treatment group, regardless of the treatment randomized. The "as treated" is determined by the first dose subject will receive for Period A, and is determined by the first dose subject will receive for Period B.

## 5.0 Subject Disposition

The total number of subjects who were screened, randomized, and treated will be summarized. Reasons for exclusion, including screen failure, will be summarized.

A summary of subject accountability will be provided where the number of subjects in each of the following categories will be summarized for each treatment group:

- Subjects randomized in the study;
- Subjects who took at least one dose of study drug;
- Subjects who completed study;
- Subjects who prematurely discontinued study drug (all reasons and primary reason);
- Subjects in each analysis population, as applicable.

For end of study participation, the number and percentage of subjects who completed each treatment period (or did not with associated reasons) will be summarized overall and by treatment group.

## **6.0 Study Drug Duration and Compliance**

For safety population, duration of treatment for each treatment period will be summarized for each treatment group and for all investigational study drug dose groups combined.

### **Study Drug Exposure (in Days) in Each Period:**

In Period A, duration of treatment is defined as:

- For subjects who did not continue to Period B,
  - last injection date in Period A minus first injection date in Period A + 84 days.
- For subjects who continued to Period B, the minimum of
  - last injection date in Period B minus first injection date in Period A,
  - last injection date in Period A minus first injection date in Period A + 84 days.

In Period B, duration of treatment is defined as:

- last injection date in Period B minus first injection date in Period B + 84 days.

For ALL\_RZB population, duration of treatment is defined as

- date of last injection of risankizumab minus date of first injection of risankizumab + 84 days.

Duration of treatment will be summarized using the number of subjects treated, mean, standard deviation, median, minimum and maximum.

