### **2.2 Study Design Overview**

This is a Phase 2, global, randomized, double-blind, placebo-controlled multicenter study that will evaluate the efficacy and safety of two dose levels, 150 mg and 300 mg respectively, of risankizumab in adult ( $\geq 18$  years of age) and adolescent (12 - 17 years of age) subjects with a confirmed diagnosis of moderate to severe AD and onset of symptoms at least 2 years prior to the Baseline Visit.

This study is comprised of an approximately 35-day screening period, a 16-week Double Blind (DB) Treatment Period A, a 36-week DB Treatment Period B, and a 20-week (140 days) Follow-up Visit.

[figure not shown]
- Period A (Baseline/Week 0 – Week 16) is a 16-week double-blind, placebo-controlled treatment period. Subjects who meet the study's eligibility criteria (Protocol Section 5.1) will be randomized at the Baseline visit to receive risankizumab 150 mg, risankizumab 300 mg or matching placebo. Study drug administration for Period A will occur at Weeks 0 and 4. The last visit in Period A is planned at Week 16 when all scheduled efficacy and safety assessments will be performed.
- In Period B (Week 16 – Week 52), subjects receiving placebo in Period A will be re-randomized at Week 16 to receive risankizumab 150 mg or risankizumab 300 mg through Week 52. Subjects originally randomized to risankizumab 150 mg or 300 mg in Period A will stay on their previously assigned treatment through Week 52. Study drug administration for Period B will occur at Weeks 16, 28 and 40.
- A follow-up telephone call visit will occur 140 days after the last dose of study drug to determine the status of any ongoing AEs/SAEs or the occurrence of any new AEs/SAEs and use of any concomitant medications.

During Period B, subjects with < EASI 50 response as compared to Baseline at the most recent prior and current scheduled visits will be allowed to use approved concomitant rescue treatment as early as at Week 24 and at any visit thereafter. Rescue treatment is limited to up to twice-daily application of topical corticosteroids.

The primary analysis will be conducted after all ongoing subjects have completed Week 16. The Week 16 evaluation is the final analysis for the primary endpoint of EASI 75 and key secondary endpoints of vIGA-AD response and worst pruritus NRS 4 point reduction. The study sites and subjects will remain blinded to treatment assignments for the duration of the study.

The schematic of the study is shown in [Figure 1](#).

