### **TEAEs for Period A:**

For subjects who do not enter Period B, TEAEs are defined as any event with an onset or worsening date on or after the first dose of study drug and no more than 140 days after the last dose of study drug.

For subjects who enter Period B, TEAEs are defined as any event with an onset or worsening date on or after the first dose of study drug in Period A and before the first dose of study drug in Period B.

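### SAP Section 6.0 caps Period A treatment duration at the last, not the first, Period B injection, so the cap does nothing for subjects with two or more Period B doses

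*SAP*

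**What the plan says.** SAP Section 6.0 (Study Drug Exposure) defines duration of treatment separately for each period. For subjects who continue to Period B, Period A duration is the minimum of:

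- term 1: "last injection date in Period B minus first injection date in Period A";
- term 2: "last injection date in Period A minus first injection date in Period A + 84 days".

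Period B duration is "last injection date in Period B minus first injection date in Period B + 84 days", so it starts at the first Period B injection. For the all-risankizumab population the duration is "date of last injection of risankizumab minus date of first injection of risankizumab + 84 days".

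The dosing calendar is in SAP Section 2.2: "Study drug administration for Period A will occur at Weeks 0 and 4", and "Study drug administration for Period B will occur at Weeks 16, 28 and 40". Period A "is a 16-week double-blind, placebo-controlled treatment period".

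In SAP Section 9.2.1, the Period A adverse event window for the same subjects closes "before the first dose of study drug in Period B".

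**The concern.** A minimum is useful only if each term can be the smaller one for some subjects. The natural purpose of term 1 is to stop Period A exposure when Period B treatment begins. That moment is the first Period B injection, which is also where Section 6.0 starts Period B duration and where Section 9.2.1 closes the Period A event window. Term 1 names the last Period B injection instead, planned for Week 40.

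If term 1 cannot be selected, nothing ends Period A at the Week 16 dose. Some days may then be counted in both periods. For a subject randomized to placebo, those days follow the first risankizumab dose but would be summarized as placebo treatment. The same completed Period A could also receive different durations at different data cuts.

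**Working it through.** **Inputs** (first Period A injection = Day 0)

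- Planned doses, SAP Section 2.2: Days 0 and 28 in Period A; Days 112, 196 and 280 in Period B.
- Windows, Protocol Appendix D and Operations Manual Section 2.1: Week 4 is Day 25 to 31; Week 16 is Day 109 to 115; Week 28 is Day 189 to 203.

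**Formulas**

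- As written: min(last B − first A, last A − first A + 84).
- With the first Period B injection: min(first B − first A, last A − first A + 84).

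**1. Planned schedule.** The SAP gives no expected duration, so the only figure to check against is the 16-week length of Period A, 112 days. As written: min(280, 28 + 84) = 112. With the first injection: min(112, 112) = 112. Both reproduce it. Period B is 280 − 112 + 84 = 252, and 112 + 252 = 364, equal to the all-risankizumab duration of 280 + 84 = 364 for a subject on risankizumab throughout. Overlap is zero.

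**2. Can term 1 be selected?** With two or more Period B injections, the last is no earlier than Day 189 in window. Term 2 is at most 31 + 84 = 115. Since 189 > 115, term 1 is never the minimum (0 of the 7 × 15 = 105 combinations of Week 4 day and Week 28 day). With exactly one Period B injection, last and first are the same date, and term 1 binds in 21 of the 7 × 7 = 49 combinations of Week 4 and Week 16 day.

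**3. Size of the overlap with two or more Period B injections.** Overlap = max(0, last A + 84 − first B).

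| Case | As written | With first injection | Overlap |
|---|---|---|---|
| Week 4 Day 28, Week 16 Day 112 | 112 | 112 | 0 |
| Week 4 Day 31, Week 16 Day 109 (widest in-window case) | 115 | 109 | 6 |
| Week 4 Day 25, Week 16 Day 115 | 109 | 109 | 0 |
| Week 4 dose missed, Week 16 Day 112 | 84 | 84 | 0 |

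In the second row, with the last dose on Day 280, Period B is 280 − 109 + 84 = 255. The two periods then sum to 115 + 255 = 370, against 364 for the all-risankizumab duration.

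Let the Week 4 and Week 16 deviations be a and b days, each from −3 to +3. Overlap is max(0, a − b). It is positive in 21 of 49 combinations. Gaps of 1 to 6 days occur 6, 5, 4, 3, 2 and 1 times, a total of 56 days. If deviations are uniform and independent (an assumption), the mean is 56/49 = 1.1 days, about 1% of 112.

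**4. Out-of-window dosing (assumed).** If the Week 4 dose is k days late and Week 16 stays on Day 112, term 2 is 112 + k and overlap is k days. For k = 7, 14, 21 and 28 the formula gives 119, 126, 133 and 140 days instead of 112.

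**5. Dependence on the data cut.** Take the subject dosed on Days 31 and 109. With only the Week 16 dose in Period B, duration is min(109, 115) = 109. Once the Week 28 dose is given, say on Day 196, it becomes min(196, 115) = 115, although nothing in Period A has changed.

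**The case against.** Little is at stake if the trial runs to plan. The 84-day term alone ends Period A on Day 112 when doses are on schedule, a missed Week 4 dose leaves no overlap, and 28 of the 49 in-window combinations give none. Six days is the single widest in-window case. Larger overlaps need dosing outside the windows; the documents give no frequency for it, and Operations Manual Section 3.17 requires sponsor consultation before an out-of-window visit. All of this stands, and it limits the size of the problem. It does not make term 1 right: nothing elsewhere in the SAP corrects it, and overlap can occur without any departure from the visit windows.

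A reader might infer three stronger conclusions that the documents do not support.

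- *The cap never works.* It does for a continuing subject with a single Period B injection, including anyone who has had only the Week 16 dose when the primary analysis is cut.
- *Placebo adverse event rates are distorted.* SAP Section 9.2.4 defines its own exposure for rates per 100 patient-years, from first to last dose plus 140 days. Term 1 does not enter it.
- *The error breaks an alignment between Period A exposure and the Period A event window.* There is no such alignment. Subjects who do not continue have exposure to 84 days after the last dose but an event window to 140 days. Continuing subjects dosed more than 84 days after their last Period A dose stop accruing exposure before their event window closes. Both differences would remain after correction. Section 9.2.1 is useful here only as evidence of where the SAP places the start of Period B.

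**Conclusion.** Wrong as written, with a small effect. For subjects with two or more in-window Period B injections, term 1 cannot bind and Period A duration is not capped at the start of Period B. Duration is overstated only when the Week 16 dose falls less than 84 days after the last Period A dose. The overstatement is 0 days on the planned schedule and at most 6 within windows (115 against 109, or 6/109 = 5.5%), averaging about 1.1 days under the uniform and independent assumption. An assumed Week 4 delay of 7 to 28 days with Week 16 on time gives 7 to 28 days.

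The effect is confined to the descriptive duration-of-treatment summary. Because that summary reports the maximum as well as the mean, single out-of-window cases would show. Early enrollees may have several Period B doses when the Week 16 analysis is cut and late enrollees only one, so the figure could also differ between the Week 16 and final reports. Period B and all-risankizumab durations, adverse event rates, efficacy, multiplicity control and power are untouched.

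**What to change.** In SAP Section 6.0, in the first term of the Period A minimum for subjects who continue, change the Period B date from the last injection to the first, so that the term is first Period B injection minus first Period A injection. Leave the second term as it is. Period A duration then cannot run past the first Period B dose, and it no longer depends on how many Period B doses have been given at the data cut. The cost is one word in the SAP and one line of code.

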### **Compliance**

There will be a summary of the number of subjects receiving study drug at each study drug administration visit during each treatment period. This will be repeated on the cumulative number of doses.

When computing compliance at each study drug administration visit, the denominator will include all subjects in each analysis population who have not prematurely discontinued the study drug prior to the scheduled study drug injection. Subjects who have prematurely discontinued the study drug but have not prematurely discontinued the study are not used in the denominator.

## **7.0 Demographics, Baseline Characteristics, Medical History, and Prior/Concomitant Medications**

Demographics, baseline or disease characteristics, medical history, and prior and concomitant medications will be summarized for the ITT population by treatment group and overall. Categorical variables will be summarized with the number and percentage of subjects; percentages will be calculated based on the number of non-missing observations. Continuous variables will be summarized with descriptive statistics (number of non-missing observations, mean and standard deviation, median, minimum and maximum).

### **7.1 Demographics and Baseline Characteristics**

The following demographic and baseline characteristics will be summarized.

### **Subject Demographics**

- Continuous demographic variables include age, weight, height, and body mass index (BMI).
- Categorical demographic variables include
  - Sex (male, female)
  - Ethnicity (Hispanic or Latino, Other)
  - Race (White, Black, Asian, American Indian or Alaska Native, Native Hawaiian or Other Pacific Islander, Multi Race)
  - Age categories (< 18 or ≥ 18 years; < 18, ≥ 18 - < 40, ≥ 40 – < 65, or ≥ 65 years),
  - BMI category (< 25, ≥ 25 – < 30, or ≥ 30 kg/m^2)
  - Geographic region (Japan or rest of world)

### **Disease Characteristics**

- Continuous variables including the baseline assessment of the following:
  - EASI overall score and body region scores
  - vIGA-AD score
  - Worst pruritus Numerical Rating Scale (NRS)
  - Body Surface Area (BSA) in percentage
  - Scoring Atopic Dermatitis (SCORAD)
  - Dermatology Life Quality Index (DLQI)
  - Children's Dermatology Life Quality Index (CDLQI)
  - Patient Oriented Eczema Measure (POEM)
  - Patient Global Impression of Severity (PGIS)
  - Patient Global Impression of Change (PGIC)
  - EuroQoL Dimensions 5 Levels (EQ-5D-5L)
  - Atopic Dermatitis Symptom Scale (ADerm-SS) 7-item total symptom score (TSS-7)
  - ADerm-SS 11-item total symptom score (TSS-11)

- ADerm-SS skin pain score
- Atopic Dermatitis Impact Scale (ADerm-IS) domain scores (sleep, emotional state, daily activities)
- AD disease duration since diagnosis (years),
- AD disease duration since symptoms started (years),
- duration between symptoms and diagnosis of AD disease (years)
- Categorical variables including:
  - Baseline vIGA-AD score (< 4, 4)
  - Baseline vIGA-AD score (0, 1, 2, 3, 4)
  - Baseline EASI (< median, ≥ median)
  - Baseline Electrocardiogram (ECG) categories, including normal, abnormal – not clinically significant, abnormal – clinically significant, unable to evaluate, and details of the abnormality when applicable.
  - Intrinsic/non-allergic subtype (IgE level < 200 kU/L, IgE level ≥ 200 kU/L)
  - Treatment-emergent ADA status during Week 0 to Week 16 (yes, no)
  - Treatment-emergent NAb status during Week 0 to Week 16 (yes, no)
  - Tobacco user (current, former, never, unknown)
  - Alcohol user (current, former, never, unknown)

